Infusion will be stopped when:

- Allergic reaction is aroused after the product has been administered intravenously.
- Patient verbally decline the treatment at any moment prior, or during the infusion.
- Hyperpyrexia develops after infusion administration begins (core body temperature greater than or equal to 40°C) [57].
- PI may stop the study at any time, based upon PI's discretion
- Malignant Hypertension (180/120 mm/Hg)
- Sudden Severe Hypotension (30-40 mm/Hg drop from pre-infusion level)

Study Alteration Rules

If any of the following events listed below occur, administration of the study drug will be immediately suspended. The Internal Monitoring Committee (IMC), presided by the Medical Monitor will meet to review the incident and its etiology. The committee determine if it is likely related to the drug, the infusion or unrelated. If the IMC along with the Medical Monitor agree that the SAE is unlikely or unrelated to the drug, the study will be continued. If the SAE appears to be definitely drug-related, the study will be stopped. If the SAE is probably or possibly linked to the drug, the IMC will determine the risk to future patients and decide if the study should proceed or be stopped.

Study Stopping Rules

The stopping rules listed below will trigger cessation of enrollment and potential study closure pending a comprehensive DSMB safety review.

1. Any infusion related death deemed by PI to be associated or possibly associated with study drug.
2. Three or more of the same Grade 3 or higher AEs (judged by the investigator, medical monitor or sponsor), including infusion site reactions.
3. Any event which, in the opinion of the investigator, medical monitor or sponsor, contraindicates further dosing of additional subjects.
4. An infusion related, sustained (over 1 minute) episode of hypoxia (SaO₂ of less than 80%).
5. Any Grade 4-5 Adverse Event as defined in the NCI CTCAE v4.0 and determined to be temporally related to the HB-adMSCs infusion by the Medical Safety Monitor and/or DSMB.

After such review, resumption of dosing may be considered, including consideration for any prophylactic interventions (e.g. antihistamines or corticosteroids for injection site reactions).

Medical Monitoring

Allogeneic HB-adMSCs to provide immune support against COVID-19.

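### For a serious event that meets a stopping rule, the Study Alteration Rules and Study Stopping Rules give different outcomes, and nothing ranks the IMC's decision against the DSMB review

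*Protocol*

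**What the plan says.** Both sections are in the protocol, one directly after the other.

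**Study Alteration Rules.** The section opens: "If any of the following events listed below occur, administration of the study drug will be immediately suspended". No events are listed under that heading. It then names the reviewing body: "The Internal Monitoring Committee (IMC), presided by the Medical Monitor will meet to review the incident and its etiology". Three outcomes follow:

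- Unrelated or unlikely to be related: "If the IMC along with the Medical Monitor agree that the SAE is unlikely or unrelated to the drug, the study will be continued".
- Definitely related: "If the SAE appears to be definitely drug-related, the study will be stopped".
- Probably or possibly related: "the IMC will determine the risk to future patients and decide if the study should proceed or be stopped".

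**Study Stopping Rules.** This section has its own lead-in: "The stopping rules listed below will trigger cessation of enrollment and potential study closure pending a comprehensive DSMB safety review". Five numbered triggers follow. Rule 1 covers an infusion-related death that the PI considers associated, or possibly associated, with study drug. Rule 5 covers a Grade 4-5 adverse event that the medical safety monitor and/or the DSMB finds temporally related to the infusion. The section closes: "After such review, resumption of dosing may be considered".

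**The concern.** The Alteration Rules point to a list that is not under their heading, and the only list that follows belongs to a different procedure. A serious adverse event that meets one of the five stopping triggers may therefore fall under both sections. One lets an internal committee conclude that the trial goes on, or requires that it end. The other sends the event to the DSMB with the outcome open.

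After such an event, site staff and the sponsor need to know three things at once: whether an IMC conclusion settles the matter or waits for the DSMB, whether dosing as well as enrolment is on hold, and who may authorise a restart. The protocol's Risks section says that the risks of this product in this population are not yet known, so these are questions to settle before an event occurs.

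**Working it through.** No arithmetic applies and the plan gives no figure to reproduce. The check sets the two sections side by side and traces example events through each.

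**Step 1. What the missing list could be.** There are two readings, and only one can be true.

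- Reading A: the events meant are the five stopping triggers. Each trigger then falls under both procedures.
- Reading B: a separate list was intended and is absent. The Alteration Rules then have no stated trigger. Overlap with the Stopping Rules would be avoided only if that list left out every SAE that meets a stopping rule, and nothing in the documents says so.

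**Step 2. Whether an SAE can meet a stopping rule.** It can. The protocol's SAE definition includes fatal and life-threatening events. Rule 1 is a death and rule 5 covers Grade 4-5 events.

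**Step 3. The two procedures compared.**

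| | Study Alteration Rules | Study Stopping Rules |
|---|---|---|
| Trigger | Events not listed under the heading | Five numbered triggers |
| Immediate action stated | Study drug suspended | Enrolment ceases |
| Who reviews | IMC, chaired by the Medical Monitor | DSMB |
| Basis for outcome | Relatedness to the drug | Varies by trigger; temporal relation is enough for rule 5 |
| Outcome | Continue, stop, or IMC decides | Potential closure pending review |
| DSMB step | None mentioned | Required |
| Resumption | Study continues if unlikely or unrelated | May be considered after the review |

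**Step 4. Example events traced through both.**

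- *Grade 4 SAE, temporally related to the infusion, judged unlikely to be drug-related by the IMC and Medical Monitor.* Alteration Rules: the study is continued. Stopping rule 5: enrolment ceases, with potential closure pending DSMB review. The Alteration Rules are the more permissive here.
- *Infusion-related death that the PI considers associated with study drug and that the IMC finds definitely drug-related.* Alteration Rules: the study is stopped, with no alternative. Stopping rule 1: closure is potential, and dosing may be resumed after review. Here the Alteration Rules are the stricter.
- *Infusion-related death that both the PI and the IMC consider possibly related.* Alteration Rules: the IMC decides whether to proceed. Stopping rule 1: enrolment ceases pending DSMB review. Whether the IMC may decide before, after or without that review is not stated.

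**Step 5. Whether another section breaks the tie.**

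- Staggering: the DSMB must permit further dosing after the first 4 patients have had their second infusion. This is a single early gate.
- Infusion Stopping Rules: the PI may stop the study at discretion.
- Medical Monitoring: a physician at the sponsor reviews AEs and SAEs to determine whether the study should be stopped, and the DSMB reviews all deaths and several other event types.
- SAP Section 8: safety summaries only, with no stopping procedure.

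None of these places the IMC's conclusion above or below the DSMB review. The IMC is not mentioned anywhere else in either document.

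**The case against.** The strongest defence is that the sections interlock. On Reading A, the Alteration Rules suspend dosing, the Stopping Rules halt enrolment, and the closing sentence about resuming dosing presupposes the suspension that only the Alteration Rules order. The IMC would be a first tier and the DSMB a second. Much of this stands, and it rules out several stronger readings that a reader might infer.

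- *That the two immediate actions contradict each other.* They do not. Suspending drug and ceasing enrolment can both apply to one event.
- *That enrolled participants would go on being infused while the event is reviewed.* The text does not support this. On Reading A, drug is suspended at once. On Reading B, the point is unstated, although the reference to resumption implies a halt.
- *That two bodies hold rival powers of decision.* The text gives the DSMB a review and does not say who decides on resumption.
- *That the IMC can plainly restart dosing without the DSMB.* For the five triggers, resumption is placed after the DSMB review, and Medical Monitoring sends all deaths and several other event types to the DSMB in any case.
- *That the causality terms make the rule unworkable.* The IMC's terms unlikely and probably are not on the protocol's three-level scale, but each shares its outcome with a neighbouring term, so the mismatch changes no result.
- *That the list is missing and also that the same events carry two procedures.* These are alternatives and cannot both be counted.

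It is also fair to say that resumption is only permitted, and that the stopping triggers are wider than definitely related SAEs, so the resumption clause could be meant for the other cases.

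The defence fails on the outcomes. The instructions to continue or to stop are worded as conclusions, not as referrals, and no sentence makes them subject to the DSMB review. The tiered arrangement is plausible, but the protocol does not state it.

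**Conclusion.** The concern holds as an internal contradiction of wording. For an SAE that meets a stopping rule, the Alteration Rules can continue the study or require that it stop with no DSMB step. The Stopping Rules make the same event a matter of halted enrolment, potential closure and DSMB review. The clearest case is the Grade 4 SAE that is temporally related to the infusion but judged unlikely to be drug-related. The definitely related SAE shows the conflict in the other direction.

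There is no numerical size. The consequence is uncertainty over authority and over the status of dosing at the moment when a serious event has occurred, which bears on participant safety and should be resolved.

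The conclusion assumes that no event list under the Alteration Rules was lost when the text was extracted. The lists on either side are intact and no gap is marked, so loss is unlikely but cannot be excluded. A recovered list would remove the conflict only if it excluded every SAE that meets a stopping rule.

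**What to change.** Reconcile the two sections so that they state:

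1. which events the Alteration Rules refer to, either by pointing to the five stopping triggers or by supplying the separate list;
2. for each trigger, whether dosing as well as enrolment is halted;
3. whether an IMC decision to continue or to stop is subject to the DSMB review;
4. who authorises resumption.

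Which clinical rule applies to which event is for the sponsor and DSMB to choose; no view is offered here. The cost is wording only. Sample size, visit schedule and SAP analyses are unaffected.

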to the HB-adMSCs and Placebo groups, respectively. Safety assessments will be ongoing. Complete Blood Count, Comprehensive Metabolic Profile and Coagulation Panel will screen for hepatotoxicity, renal failure or alterations in the coagulation cascade that might entail a safety concern for the individual. Efficacy assessments will include PHQ-9, SF-36, TNF-a, IL-6, IL-10, and CRP.

The trial is designed to be conducted over 3 periods or phases:

- **Phase 1** (screening): Our screening process starts with a telephone call to provide a general overview of the study and discuss eligibility requirements. The study patient will receive the informed consent document by e-mail or in the pre-paid envelope provided. If, after reviewing this consent the study patient is still interested in participating in the study, he/she will need to sign and return the consent form to Hope Biosciences Stem Cell Research Foundation. This process can take up to 45 days.
- **Phase 2** (Treatments): Includes Infusion 1 (Week 0), Infusion 2 (Week 2), Infusion 3 (Week 6), Infusion 4 (Week 10) and Infusion 5 (Week 14). Subjects will be monitored at the clinical site for 1 hours following HB-adMSCs administration.
- **Phase 3** (follow-up): Includes Follow Up Week 18, 22 and End of Study at Week 26.

Selection and Withdrawal of Patients

Inclusion Criteria

Inclusion Criteria:

1. Men, and women 18 years of age or older
2. Participant works in a capacity that is characterized as high-risk or very high-risk
 - a. High-Risk Exposure jobs are those with high potential for exposure to known or suspected sources of COVID-19.
 - First responders, health care delivery and support staff (e.g., law enforcement, fire fighters, paramedics, doctors, nurses, and other hospital staff who must enter patients' rooms) exposed to individuals potentially having COVID-19.
 - Mortuary workers involved in preparing (e.g., for burial or cremation) the bodies of people who are known to have, or suspected of having, COVID-19 at the time of their death
 - b. Very High-Risk Exposure jobs are those with high potential for exposure to known or suspected sources of COVID-19 during specific medical, postmortem or laboratory procedures.
 - Health care workers (e.g., doctors, nurses, dentists, paramedics, emergency medical technicians) performing aerosol-generating procedures (e.g., intubation, cough induction

Allogeneic HB-adMSCs to provide immune support against COVID-19.

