Allogeneic HB-adMSCs to provide immune support against COVID-19.

Details of the investigational product

Allogeneic HB-adMSCs is to be administered as an IV infusion with a syringe containing 5×10^7 cells. Each syringe will be provided by Hope Biosciences on the day of the infusion after all quality control assays have been performed and the results are within normal range.

Instructions for Administration

The designated study staff will administer the investigational product in the following manner:

- Prior to administration, visually inspect the infusion solution for particulates. If foreign particles are present, do not use the solution.
- Emergency equipment, such as epinephrine, antihistamines, and corticosteroids must be available in the event of infusion-related reactions.
- Start IV administration after dilution.
- Administer the infusion solution over a period of 1h. Observe the patient for at least 2 hours post-infusion for acute infusion-related reactions, including anaphylaxis. See Appendix 1 for guidelines on diagnosing anaphylaxis.
- Do not store or reuse any unused portion of the infusion solution. Any unused product or waste material should be disposed.
- Volume of study drug infused, start times, and stop times will be recorded. If any portion of the infusion (cell solution) is discarded, the reason will be recorded in the CRF.
- The patient will be monitored for a total of 3 hours from drug exposure to discharge.
 - a. During the Investigational product administration (1 hour) vital signs will be measured at minute 0, 15, 30 and 45.
 - b. Post infusion, vital signs will be measured at minute 0, 30 and 60.

Investigational Product Assignment and Infusion Schedule (Randomization and Staggering)

Randomization

A total of 53 eligible subjects will be randomized to either placebo or treatment group within the associated study arm at baseline. Randomization will determine whether the subject receives placebo or HB-adMSCs.

A neutral, third-party personnel will be responsible for assigning the participants' treatment group. This role will be referred to as 'randomizer'. The designated personnel from the drug manufacturer will be responsible in labeling and packaging the investigational product for each participant. This role will be referred to as 'mixer'. Participants' names are not disclosed to the mixer and the unblinded information will only be known to the randomizer.

Staggering

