- Concomitant medications will be reviewed and updated if necessary.
- Medical History will be reviewed and updated if necessary. If the patient reported a medication which does not match the current medical history, further investigation will be required to determine whether it was an Adverse Event, or the patient just forgot to mention it before. If it is found to be an AE, it should be recorded in the appropriate CRF. If the patient forgot to mention it before, a note to file (NTF) should be made to clarify the case.
- Blood samples will be collected for laboratory assessments at weeks 0, 2, 6, 10, 14, and 26.

Allogeneic HB-adMSCs to provide immune support against COVID-19.

- Pre-infusion medications: Prior to IP administration the subject will be administered: Aspirin 81 mg per mouth, and Loratadine 10 mg per mouth
- Physical examination performed by principal investigator or sub-investigator.
- Patient will complete SF-36 and PHQ-9 assessments.
- Administer investigational product.
- Monitor for AEs. Observe the patient for at least 1 hour after infusion for symptoms of infusion-related reactions and allergic reactions, including anaphylaxis (See Appendix 1).
- Instruct the patient on recognition of delayed serious allergic reactions, including anaphylaxis and seeking for medical assistance.
- Telephone encounter 24 hours after the infusion will be performed to assess the occurrence of AEs.

Follow Up Weeks 18, and 22.

- Weight will be measured
- Vital Signs will be measured.
- Concomitant medications will be reviewed and updated if necessary.
- Medical History will be reviewed and updated if necessary. If the patient reported a medication which does not match the current medical history, further investigation will be required to determine whether it was an Adverse Event, or the patient just forgot to mention it before. If it is found to be an AE, it should be recorded in the appropriate CRF. If the patient forgot to mention it before, a note to file (NTF) should be made to clarify the case.
- Physical examination performed by principal investigator or sub-investigator.
- Patient will complete SF-36 and PHQ-9 assessments.
- Instruct the patient on recognition of delayed serious allergic reactions, including anaphylaxis and seeking for medical assistance.
- Telephone encounter 24 hours after the infusion will be performed to assess the occurrence of AEs.

Weeks 26 (End of the Study or Early Discontinuation Visit)

- Weight will be measured

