The PHQ-9 is the depression module, which scores each of the nine DSM-IV criteria as "0" (not at all) to "3" (nearly every day). It is not a screening tool for depression, but it is used to monitor

Allogeneic HB-adMSCs to provide immune support against COVID-19.

the severity of depression. In addition to making criteria-based diagnoses of depressive disorders, the PHQ-9 is also a reliable and valid measure of depression severity.

TNF- α

The primary role of TNF is in the regulation of immune cells. TNF, being an endogenous pyrogen, is able to induce fever, apoptotic cell death, cachexia, inflammation and to inhibit tumorigenesis and viral replication and respond to sepsis via IL1- & IL6-producing cells.

IL-10

IL-10 is a cytokine with multiple effects in immunoregulation and inflammation. It downregulates the expression of Th1 cytokines, MHC class II antigens, and co-stimulatory molecules on macrophages. It also enhances B cell survival, proliferation, and antibody production.

IL-6

Interleukin 6 (IL-6) is an interleukin that acts as both a pro-inflammatory cytokine and an antiinflammatory myokine. In humans, it is encoded by the *IL6* gene.

Safety Assessments

Safety assessments (vital signs, weight, physical examinations, AEs, routine clinical laboratory tests (CBC, CMP, PT and PTT/INR) will be performed at the visits specified in the schedule of assessments in Table 2.

Vital Signs, Height, and Weight

Vital signs (body temperature, pulse, oxygen saturation, systolic and diastolic blood pressure measurements) will be evaluated at the visits indicated in the schedule of assessments. It is important that all vital signs be measured after the patient has been resting in a sitting position for at least 5 minutes. Blood pressure measurements are to be taken in the same arm for the duration of the study. Body weight (without coats and shoes) will be recorded whenever vital signs are recorded, and height (without shoes) will be recorded at Infusion 1 (baseline) only.

Vital sign measurements will be repeated if clinically significant or machine/equipment errors occur. Out-of-range blood pressure and pulse measurements will be repeated at the Investigator's discretion. Any confirmed, clinically significant vital sign measurements will be recorded as AEs and followed up as such.

Physical Examination

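### Stopping rule 4 turns on a saturation fall lasting over 1 minute, but stated readings in the infusion hour are 15 minutes apart, and the post-infusion watch is given as both 1 and 2 hours

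*Protocol*

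**What the plan says.** **The trigger.** Rule 4 of the protocol's Study Stopping Rules is "An infusion related, sustained (over 1 minute) episode of hypoxia", with the threshold set at saturation below 80%. One such episode stops enrolment pending a DSMB safety review.

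**The readings.** The section Vital Signs, Height, and Weight makes saturation part of every vital-sign set: "Vital signs (body temperature, pulse, oxygen saturation, systolic and diastolic blood pressure measurements". Instructions for Administration gives the timing. During the 1-hour infusion, "vital signs will be measured at minute 0, 15, 30 and 45". Afterwards, "Post infusion, vital signs will be measured at minute 0, 30 and 60".

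**The watch.** Four places give its length:
- Instructions for Administration: "Observe the patient for at least 2 hours post-infusion", and "The patient will be monitored for a total of 3 hours from drug exposure to discharge".
- Respiratory Risks: saturation and breathing are to be monitored for the first 2 hours after the infusion. No mode or frequency is given.
- Investigational Plan, treatment phase: "Subjects will be monitored at the clinical site for 1 hours following HB-adMSCs administration".
- Infusion Visits: "Observe the patient for at least 1 hour after infusion".

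No section specifies continuous oximetry. The SAP does not address the point.

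**The concern.** The trigger is measured in minutes and the written readings in quarter-hours or half-hours. A fall that meets rule 4 could begin and end between two readings and leave no value on record.

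This matters here because Respiratory Risks names an infusion-triggered thromboembolic event with respiratory failure as a potential risk. Rule 4 is also the only stop that names saturation. The clinical triggers in the Infusion Stopping Rules are allergic reaction, temperature and blood pressure, alongside patient refusal and investigator discretion.

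The second problem is the length of the watch. A site that follows the Investigational Plan could discharge patients halfway through the 2 hours that Instructions for Administration requires.

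**Working it through.** **1. The plan's own total.** A 1-hour infusion plus at least 2 hours of observation gives 1 + 2 = 3 hours, which agrees with Instructions for Administration.

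**2. Readings on one clock.** Take the infusion as exactly 60 minutes, so that post-infusion minute 0 is minute 60. The timed readings then fall at 0, 15, 30, 45, 60, 90 and 120 minutes. The gaps are 15, 15, 15, 15, 30 and 30 minutes. No timed reading follows between minute 120 and minute 180.

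**3. Infusion hour.** The documents give no episode length, so a range is used. For a fall of L minutes with onset uniform over the hour, and counting timed readings only, the chance that a reading lands inside it is P = min(L, 15)/15.

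| L (minutes) | P |
|---|---|
| 2 | 2/15 = 13% |
| 5 | 5/15 = 33% |
| 10 | 10/15 = 67% |
| 15 | 15/15 = 100% |

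A fall of 15 minutes or more that starts in this hour therefore always meets a timed reading.

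**4. First post-infusion hour.** The same reasoning with 30-minute spacing gives P = min(L, 30)/30. For 2, 5, 10 and 15 minutes this is 7%, 17%, 33% and 50%. These are floors: they count none of the saturation monitoring planned under Respiratory Risks. If that monitoring is continuous, this gap closes.

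**5. Second post-infusion hour.** No timed reading falls here, but the Respiratory Risks monitoring covers it. Its yield depends on a mode and frequency that the protocol does not state, so no detection figure can be given.

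**6. Duration.** No fall shorter than 15 minutes can span two timed readings, so scheduled values alone cannot show that it lasted over 1 minute. Once a low value is seen, however, the protocol can follow it: clinically significant vital signs are repeated, and the duration of each adverse event is recorded. The exposed case is a short fall that no reading meets.

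**7. Length of the watch.** The Investigational Plan's 1 hour has no wording that makes it a minimum, so it contradicts both the minimum of 2 hours in Instructions for Administration and the 2 hours in Respiratory Risks. The figure in Infusion Visits is a minimum. It is compatible with 2 hours but sets a lower floor.

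**The case against.** The strongest reply is that Respiratory Risks already plans saturation monitoring for 2 hours after the infusion, aimed at the very risk in question. This stands in part. A reader might infer from the timed schedule that saturation is not followed in the last hour of the watch and that a fall there has no chance of being seen. The documents do not support that, because even intermittent monitoring in that hour would give some chance. But the same passage does not reach the infusion hour, and it does not tell staff how to monitor. The only explicit schedule is the spaced one.

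A second reply is that the percentages restate the spacing under assumed episode lengths, with staff response set to zero. That is fair, and they should be read only as a description of the written schedule.

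Third, there are backstops:
- staff at the infusion, and readings prompted by symptoms;
- investigator discretion to stop;
- stopping rules 3 and 5;
- DSMB review after the second infusion of the first 4 patients;
- a call 24 hours after each infusion;
- an examination for thromboembolic events, including saturation, at each visit.

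These narrow the gap. Most of them depend on symptoms, on someone noticing, or on a later look, so they do not make the schedule fit the trigger.

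Fourth, the temperature and blood-pressure stops rest on the same spaced readings. That is true, but rule 4 is the one that sets a 1-minute duration.

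Finally, the conflict over the watch is a matter of wording. It is a separate correction and lends no weight to the percentages.

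**Conclusion.** The point holds as a cheap improvement, in two separate parts.

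First, in the infusion hour the written schedule can miss the event that rule 4 names. The chance that a timed reading meets a fall of 2, 5 or 10 minutes is 13%, 33% or 67%. This assumes uniform onset, a 60-minute infusion and no readings beyond the timed ones; extra readings would raise the figures. The gap concerns falls shorter than 15 minutes. After the infusion its size depends on how the 2-hour saturation monitoring is carried out, which the protocol leaves open.

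Second, the 1-hour watch in the Investigational Plan contradicts the 2 hours set elsewhere and needs correcting however the monitoring plan is read.

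A reader might go further and infer that rule 4 cannot work. The documents do not support that: longer falls in the infusion hour are met, a low value once seen is followed up, and the backstops remain.

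**What to change.** - In Instructions for Administration, state that pulse oximetry stays on from infusion start to the end of the 2-hour watch, with a low-saturation alarm.
- On any alarm below 80%, check the sensor and signal first. Then record the lowest value and whether it lasted over 1 minute.
- Change the Investigational Plan and Infusion Visits to at least 2 hours after the infusion.

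**Cost.** The change needs protocol wording and two CRF entries, completed only when an alarm occurs, over at most 53 × 5 = 265 infusions at one site. The documents do not describe the site's oximeter, so an alarmed device may have to be provided. Recording whether the fall passed 1 minute, rather than the exact time below 80%, avoids the need for a logging device.

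**Downside.** There will be artefact alarms and slightly more recording. Because a single episode triggers rule 4, a loose sensor could wrongly halt enrolment, so the signal check is part of the change. Chair time rises by up to 1 hour per infusion if the site now follows the Investigational Plan, and not at all if it follows Instructions for Administration.
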